8.3.6 Adverse event of special interest

Adverse event of special interest

An AESI is an AE (serious or nonserious) of scientific and medical concern specific to the Sponsor's product or program, for which ongoing monitoring and immediate notification by the Investigator to the Sponsor within 24 hours of first learning of the AESI is required. Such events may require further investigation in order to characterize and understand them. Adverse events of special interest may be added, modified or removed during a study by protocol amendment.

- Pregnancy of a female participant entered in a study as well as pregnancy occurring in a female partner of a male participant entered in a study with IMP;
 - Pregnancy occurring in a female participant entered in the clinical trial or in a female partner of a male participant entered in the clinical trial. It will be qualified as an SAE only if it fulfills one of the seriousness criteria (see Appendix 3 [[Section 10.3](#)]).
 - In the event of pregnancy in a female participant, IMP should be discontinued.
 - Follow-up of the pregnancy in a female participant or in a female partner of a male participant is mandatory until the outcome has been determined (See Appendix 4 [[Section 10.4](#)]).
- Symptomatic overdose (serious or nonserious) with IMP
 - An overdose (accidental or intentional) with SAR442720 is an event suspected by the Investigator or spontaneously notified by the participant (not based on systematic pills count) and defined as at least twice the intended dose within the intended therapeutic interval, adjusted according to the tested drug.
 - Infusion with pembrolizumab: increase of at least 30% of the dose to be administered in the specified duration or if the dose is administered in less than half the recommended duration of administration. Injectable administration: at least twice the dose during the planned intervals
 - An overdose (accidental or intentional) with adagrasib is an event suspected by the Investigator or spontaneously notified by the participant (not based on systematic pills count) and is defined as any amount above the intended dose.
- Concurrent increase in ALT and AST $>3 \times$ ULN AND total bilirubin $>2 \times$ ULN or INR >1.5 ULN in the absence of cholestasis and other causes (eg, viral hepatitis, other pre-existing or acute liver disease, or another drug capable of the observed injury), which may indicate severe drug-induced liver injury (possible Hy's law). Study drug should be withheld until AST, ALT, return to $<2 \times$ ULN and total bilirubin returns to $<1.5 \times$ ULN.
- Other project specific AESI(s)
 - QT (corrected or uncorrected) >480 msec or increased from baseline >60 msec (see [Section 7.1.1](#) QT prolongation management advice)
 - Thrombocytopenia Grade ≥ 3 or any grade if associated with clinically significant bleeding (see [Section 6.6.1.8](#) for hemorrhage management guidelines)

- Edema, including generalized/peripheral edema or facial/periorbital edema (see [Section 6.6.1.12](#) for edema management guidelines)
- All protocol defined potential or IMP related DLTs are considered as AESI, regardless of the cycle of occurrence (ie, after Cycle 1 in both escalation and expansion phases)

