Other screening tests	
Coagulation test to include prothrombin time (PT)/international normalized ration (INR) and aPTT (or partial thromboplastin time)
 
Follicle-stimulating hormone and estradiol (as needed in women of non-childbearing potential only)^c
 
Highly sensitive blood or urine human chorionic gonadotropin (hCG) pregnancy test (as needed for women of childbearing potential)^b
 
Serology: hepatitis B surface antigen (HBsAg), hepatitis B core antibody (HBcAb), and hepatitis C virus antibody. If hepatitis C virus antibody is positive, then obtain hepatitis-C RNA
 
The results of each test must be entered into the case report form (CRF).

NOTES :

- a Concurrent elevation of AST or ALT >3 x ULN AND total bilirubin >2 x ULN or INR >1.5 in the absence of cholestasis and other causes (eg, viral hepatitis, other pre-existing or acute liver disease, or another drug capable of the observed injury), which may indicate severe drug-induced liver injury (possible Hy's law case). All events with the defined biochemical abnormalities must be reported as an SAE; and study medications should be permanently discontinued.
- b Local urine testing will be standard for the protocol unless blood testing is required by local regulation or IRB/IEC. For screening a blood test is required.
- c See Appendix 4 ([Section 10.4](#)).

Investigators must document their review of each laboratory safety report.

10.3 APPENDIX 3: ADVERSE EVENTS: DEFINITIONS AND PROCEDURES FOR RECORDING, EVALUATING, FOLLOW-UP, AND REPORTING

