Hepatitis, liver function test abnormalities (AST, ALT, and/or total bilirubin)	
Grade 1: Continue both study drugs at current doses.
 
Grade 2: In Part-1, 2, and 4, continue SAR442720 and withhold pembrolizumab until adverse reactions recover to Grade 0 to 1
 
In Part-3, continue SAR442720 and reduce adagrasib one dose level.
 
Grade 3: Rule out other causes such as metastatic liver disease, concomitant drugs, infection, etc. Withhold both study drugs until improves < Grade 1, then dose reduce SAR442720 and adagrasib one dose level (in Part-3) and resume pembrolizumab at the same dose (Part-1, 2 and 4). If AE does not improve or recurs, dose reduce another dose level of SAR442720. No dose modification required for isolated GGT. In Part-1, 2, and 4 hold SAR442720; if no improvement in LFTs after SAR442720, withhold pembrolizumab as well. If Grade ≥ 3 with AST or ALT occurs, permanently discontinue both study drugs.
 
In case of liver metastasis with baseline Grade 2 elevation of AST or ALT, hepatitis with AST or ALT increases $\geq 50\%$ and lasts ≥ 1 week: Permanently discontinue pembrolizumab. Action with SAR442720 or adagrasib should be discussed with the Medical Monitor.
 
Grade 4: see general Grade 4 non-heme AEs. In Part-1, 2, and 4 hold both SAR442720 and pembrolizumab. If resolves, restart both medications, SAR442720 at reduced dose (pembrolizumab dose reduction is not allowed). If no improvement to < Grade 1 within 4 weeks, permanently discontinue both drugs.
 
In Part-3 permanently discontinue both study drugs. Concurrent treatment-emergent / treatment related elevation of AST or ALT $> 3 \times$ ULN AND total bilirubin $> 2 \times$ ULN or INR > 1.5 in the absence of cholestasis and other causes (eg, viral hepatitis, other pre-existing or acute liver disease, or another drug capable of the observed injury), which may indicate severe drug-induced liver injury (possible Hy's law case). Both medications should be permanently discontinued.
 
If liver injury is due to other causes such as viral hepatitis, acute liver disease, or another drug capable of liver injury, evaluate the extent of liver injury (eg, albumin level, PTT, INR etc) and if considered to be severe, discontinue both medications.

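### For a possible Hy's law event, Protocol Section 8.3.6 says to withhold until recovery, while Table 22 note a and Table 27 say to discontinue permanently

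*Protocol*

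**What the plan says.** Four places in the protocol define a possible Hy's law event, and three of them set an action on treatment.

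- **Section 8.3.6 (AESI list).** The trigger is worded as "Concurrent increase in ALT and AST" above 3 x ULN, together with total bilirubin above 2 x ULN or INR above 1.5 ULN. The action is "Study drug should be withheld until AST, ALT, return to" below 2 x ULN and total bilirubin is back below 1.5 x ULN. No Part is named, and the text does not say which drug is meant.
- **Appendix 2, Table 22 note a.** The trigger is "Concurrent elevation of AST or ALT >3 x ULN AND total bilirubin >2 x ULN or INR >1.5 in the absence of cholestasis"; alternative explanations are excluded too. The action is "All events with the defined biochemical abnormalities must be reported as an SAE; and study medications should be permanently discontinued". No Part is named.
- **Appendix 9, Table 27, hepatitis and liver function row.** The trigger has the same AST-or-ALT form, restricted to treatment-emergent or treatment-related elevations. It ends "which may indicate severe drug-induced liver injury (possible Hy's law case). Both medications should be permanently discontinued".
- **Section 4.1.1 (DLT list).** The AST-or-ALT form is a DLT criterion in Part-1 and Part-3A. No action on treatment is attached to it there.

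**The concern.** A hold that ends at a stated recovery level and a permanent stop are different rules for the same finding. The protocol itself says that the finding may point to severe drug-induced liver injury. Two sites, each following a section of the protocol as written, could handle identical cases differently.

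Reporting is affected as well. SAP Table 5 has separate tables for TEAEs leading to permanent discontinuation (full, and of each drug) and for TEAEs leading to dose modification of SAR442720. The section a site follows therefore decides where the case is counted. Table 22 note a also makes every such event an SAE, whereas Section 8.3.6 defines an AESI as serious or nonserious. A site reading Section 8.3.6 alone would not learn that the event has to be reported as serious.

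**Working it through.** There is no figure to recompute. The check compares the texts and asks whether their triggers overlap.

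| Place | Transaminases | Second condition | Action on treatment | Scope |
|---|---|---|---|---|
| Section 8.3.6 | ALT and AST >3 x ULN | bilirubin >2 x ULN, or INR >1.5 ULN | withhold until AST and ALT <2 x ULN and bilirubin <1.5 x ULN | no Part named; drug not specified |
| Table 22 note a | AST or ALT >3 x ULN | bilirubin >2 x ULN, or INR >1.5 | permanent discontinuation | no Part named; study medications |
| Table 27 | AST or ALT >3 x ULN | bilirubin >2 x ULN, or INR >1.5 | permanent discontinuation | both drugs; follows a Part-3 sentence |
| Section 4.1.1 | AST or ALT >3 x ULN | bilirubin >2 x ULN, or INR >1.5 | none stated | Part-1 and Part-3A, first cycle |

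**Step 1: is it the same event?** All four carry the same exclusion (no cholestasis or other cause) and the same possible Hy's law label.

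**Step 2: do the triggers separate the two actions?** Write A for ALT >3 x ULN, S for AST >3 x ULN and B for bilirubin >2 x ULN. On the bilirubin route Section 8.3.6 needs A and S and B, while Table 22 note a needs (A or S) and B. The first set lies wholly inside the second. Every case that meets Section 8.3.6 by this route also meets note a, so it receives both instructions.

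**Step 3: the INR route.** Let u be the laboratory's upper limit for INR, which the documents do not give. Reading the Section 8.3.6 limit as 1.5 x u, it is at least 1.5 whenever u is at least 1.0. With assumed values:

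- u = 1.0 gives 1.5 x 1.0 = 1.5.
- u = 1.2 gives 1.5 x 1.2 = 1.8.
- u = 0.9 gives 1.5 x 0.9 = 1.35, and an INR between 1.35 and 1.5 would then meet Section 8.3.6 only.

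For u of 1.0 or more, the overlap is complete on this route too. The conclusion does not depend on it, because the bilirubin route is enough.

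**Step 4: does any text give one instruction precedence?**

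- Appendix 9 tells the investigator to follow the most conservative recommendation, but for a participant with several AEs that carry different recommendations. It does not address two instructions for one event.
- Section 6.6.1.6 calls for discontinuation on evidence of severe liver injury and refers to Table 27. It does not mention the recovery levels in Section 8.3.6.
- Section 7.1.1 lists grounds for definitive discontinuation and has no liver-specific criterion.

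None of these settles the conflict.

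**The case against.** The best case for leaving the text alone is that the permanent-stop rule is softer and narrower than it looks. Appendix 9 calls Tables 26 and 27 guidelines subject to clinical judgment. The Hy's law sentence in Table 27 comes directly after a Part-3 sentence, so it may be meant for Part-3 only; for Grade 4 liver abnormalities in Parts 1, 2 and 4 the same row gives a hold with a possible restart. Both points stand for Table 27. Neither applies to Table 22 note a, which names no Part and is not labelled a guideline. That note alone establishes the conflict in every Part.

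Four stronger readings are tempting and are not supported.

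- **One section allows re-treatment and another forbids it.** All three action sentences say should; the only must, in note a, concerns SAE reporting. Section 8.3.6 sits in a reporting section and never states that treatment may resume. Resumption is a natural inference from a hold with recovery levels, but only an inference.
- **An event with one raised transaminase is a DLT yet escapes AESI status.** The last bullet of Section 8.3.6 makes protocol-defined DLTs AESIs whatever the cycle, and Section 4.1.1 also treats them as AESIs with 24-hour reporting. An event that meets the DLT criterion enters by that route.
- **The conflict disturbs DLT counting throughout the study.** The DLT criteria apply to Part-1 and Part-3A only, and this criterion is met by the biochemistry whatever is then done with treatment.
- **The ALT and AST percentages for adagrasib in Section 2.3.1.4 measure the size of the problem.** They cover all treated patients, 57 of 259 of whom received a combination. They count any transaminase increase, with no bilirubin or INR condition, so they are not rates of possible Hy's law events.

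**Conclusion.** The protocol contradicts itself on the action for a possible Hy's law event and is wrong as written. This is an internal inconsistency rather than a choice of design. It rests on current text in Section 8.3.6 and Table 22 note a, with Table 27 as support, at least for Part-3. For cases that qualify through bilirubin no assumption is needed. For cases that qualify through INR the overlap is complete if the laboratory's upper limit is at least 1.0.

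The size cannot be put as a number of participants, because the documents give no rate for such events. What can be said is that each case meeting the Section 8.3.6 trigger by the bilirubin route, in any Part, receives two incompatible instructions.

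The differences in trigger wording (and against or; INR above 1.5 ULN against above 1.5) are a lesser defect, to be settled at the same time. The importance of the point rests on the conflicting actions. Because it concerns stopping treatment after a possibly severe liver injury, it should be corrected.

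**What to change.** Reconcile Section 8.3.6, Table 22 note a, Table 27 and Section 4.1.1 so that:

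- one trigger definition is used throughout, settling the and/or wording and whether the INR limit is absolute or a multiple of the ULN;
- one action is stated, or the others refer to a single place that states it;
- the text says which drugs and which Parts the action covers, including whether the Table 27 sentence is limited to Part-3;
- Section 8.3.6 says whether every such event is an SAE, as note a does.

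Which action and which trigger to adopt is a clinical decision for the sponsor, and this review takes no view on it. The cost is protocol wording; the sample size and the analyses do not change.

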6.6.1.5 Management of rhabdomyolysis or symptomatic CPK increase

Assess for other causes of CPK elevation and rhabdomyolysis such as strenuous exercise, trauma, heat-related causes, ischemia, inflammatory process, etc. For CPK elevations, rule out cardiac causes by obtaining ECG, cardiac troponin, and CK-MB fraction. Evaluate for rhabdomyolysis and potential renal compromise with a clinical examination, urinalysis, and complete blood chemistry (eg, metabolic panel). Treat according to institutional guidelines. Early IV hydration with urine alkalization provided that there are no contraindications. Nephrology consultation should be considered, as clinically indicated.

6.6.1.6 *Management of liver function abnormalities and hepatotoxicity*

Assess whether metastatic disease to the liver is contributing to liver function abnormalities and/or hepatotoxicity. Evaluate for infections or other causes of increased liver function abnormalities if appropriate. Consider imaging of the liver. Hold or dose reduce concomitant medications which may potentiate hepatotoxicity or metabolized by the liver. Evaluate extent of liver injury (eg, albumin level, PTT, INR) and if there is evidence of severe injury, then discontinue treatment (either SAR442720 and pembrolizumab or SAR442720 and adagrasib).

Please refer to [Table 27](#) for dose modifications guidelines for LFTs.

6.6.1.7 *Management of decrease in left ventricular ejection fraction*

Asymptomatic absolute decrease in LVEF from baseline $\geq 20\%$ from baseline and below LLN, withhold treatment (either SAR442720 and pembrolizumab or SAR442720 and adagrasib) for up to 4 weeks and repeat echocardiogram (ECHO) for LVEF at 2, 4, 10, and 16 weeks after treatment was withheld. Restart at reduced dose if LVEF \geq LLN and absolute decrease from baseline LVEF $< 20\%$. Permanently discontinue if symptoms if symptoms of heart failure are present.

Symptomatic reduction: In case of symptomatic systolic dysfunction with an LVEF decrease from baseline $\geq 10\%$ and/or below LLN, withhold both SAR442720 and pembrolizumab for up to 4 weeks and consider permanent discontinuation if considered causative; in Part-3 permanently discontinue SAR442720 and adagrasib.

Please refer to [Table 27](#) for dose modifications guidelines. Cardiology consultation should be considered.

6.6.1.8 *Management of hemorrhage*

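### For possible Hy's law, Protocol Section 8.3.6 allows restart after recovery where Appendix 2 and Table 27 require permanent discontinuation; the Table 27 Grade 3 AST/ALT paragraph also gives incompatible actions

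*Protocol*

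**What the plan says.** Possible Hy's law is defined in four places in the protocol, three of which also give a treatment action.

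- Section 8.3.6 (adverse events of special interest) starts from "Concurrent increase in ALT and AST" above 3 x ULN, combined with bilirubin above 2 x ULN or "INR >1.5 ULN in the absence of cholestasis and other causes". Its action is "Study drug should be withheld until AST, ALT, return to" below 2 x ULN and bilirubin is back below 1.5 x ULN.
- Appendix 2, Table 22 note a, starts from "Concurrent elevation of AST or ALT" above 3 x ULN, with bilirubin above 2 x ULN or INR above 1.5. Such events "must be reported as an SAE; and study medications should be permanently discontinued". The note carries no Part limit.
- Appendix 9, Table 27 (hepatitis and liver function row) starts from "Concurrent treatment-emergent / treatment related elevation of AST or ALT" above 3 x ULN with the same bilirubin and INR limits. Its action is "Both medications should be permanently discontinued".
- Section 4.1.1 (DLT criteria) uses the same either-transaminase trigger and INR above 1.5, and gives no dosing action beyond DLT status.

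The Grade 3 paragraph in the same Table 27 row says three things in sequence. First, both drugs are withheld until recovery and then resumed, with SAR442720 and adagrasib one level lower in Part-3 and pembrolizumab at an unchanged dose in Parts 1, 2 and 4. Second, in Parts 1, 2 and 4, SAR442720 is held, and pembrolizumab is added to the hold only if liver tests do not improve. Third, both drugs are stopped permanently if Grade 3 or higher occurs with AST or ALT; nothing says what has to accompany AST or ALT, or in which Part. The Grade 4 paragraph that follows allows hold and restart in Parts 1, 2 and 4 and requires a permanent stop in Part-3.

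**The concern.** A hold that lasts until numeric recovery limits are met is a resumption rule. A site that works from Section 8.3.6 could restart drug after an event for which Appendix 2 and Table 27 rule out restart. Nothing in Section 8.3.6 makes its instruction subordinate to the others: its QT, thrombocytopenia and edema bullets each point to a management section, while the Hy's law bullet gives its own action.

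For Grade 3 AST/ALT, an investigator in Parts 1, 2 and 4 cannot tell from Table 27 whether pembrolizumab is held at once or only later, and in any Part cannot tell whether the event ends treatment. This matters because Sections 6.6.1.1 and 6.6.1.6 send hepatic events to Table 27, so this row is the operative guidance.

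**Working it through.** No plan figure is involved. The check sets the current texts side by side.

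**Possible Hy's law**

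| Place | Transaminase limb (>3 x ULN) | INR limb | Action |
|---|---|---|---|
| Section 8.3.6 | ALT and AST | >1.5 ULN | withhold until recovery |
| Section 4.1.1 | AST or ALT | >1.5 | none stated (DLT criterion) |
| Appendix 2, note a | AST or ALT | >1.5 | SAE report, permanent stop |
| Table 27 | AST or ALT | >1.5 | permanent stop |

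Action: 1 place withholds, 2 stop permanently. Trigger: 1 place differs from 3, on both the transaminase and the INR limb.

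Take three cases, each without cholestasis or another cause.

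1. ALT and AST both above 3 x ULN, bilirubin above 2 x ULN. All definitions are met. Section 8.3.6 says withhold; note a and Table 27 say stop. This is the conflict.
2. Only one transaminase above 3 x ULN, bilirubin above 2 x ULN. Section 8.3.6 is not met, so its withhold sentence does not apply. Note a and Table 27 apply, and both say stop. There is no action conflict. Reporting is covered as well: note a requires an SAE report, and the last bullet of Section 8.3.6 makes any DLT-type event an AESI in any cycle, using the Section 4.1.1 definition.
3. Both transaminases above 3 x ULN, bilirubin not above 2 x ULN, INR just above 1.5. If the Section 8.3.6 limit means 1.5 times the INR upper limit, and that limit is assumed to be 1.1 to 1.2 (the documents give no value), the cut-off is 1.5 x 1.1 = 1.65 to 1.5 x 1.2 = 1.80. An INR between 1.5 and that cut-off again meets only the texts that stop treatment. The extra ULN may simply be a slip.

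So the narrower trigger does not create a second route to restart; the action conflict is confined to events that meet the Section 8.3.6 trigger.

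**Table 27, Grade 3 AST/ALT**

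- In Parts 1, 2 and 4 the first instruction holds pembrolizumab immediately; the second holds it only after SAR442720 has been held without improvement. Both cannot be followed.
- The third instruction, read literally, stops both drugs for every Grade 3 event and so cancels the first two.
- Because it covers Grade 3 or higher, it also reaches Grade 4, where the same row allows restart in Parts 1, 2 and 4.
- The nephritis row uses the same sentence form but attaches a creatinine threshold to its grade. No counterpart is visible after AST or ALT.

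**Frequency**

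Section 2.3.1.1 gives any-grade AST increase of 20.4% with SAR442720 monotherapy. Section 2.3.1.4 gives adagrasib-attributed ALT and AST increases of 16.2% and 14.7%. No Grade 3 or higher transaminase rate and no Hy's law rate is given, so no event count can be derived.

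**The case against.** The strongest reply is that Section 8.3.6 defines and routes events of special interest, while dosing is governed by Section 6.6 and Table 27. An event there is notified within 24 hours, and under note a it is also an SAE on the same clock, so the sponsor would normally know of it well before recovery. An unnoticed restart is possible but unlikely. That stands as mitigation. It does not remove the conflict, because Section 8.3.6 does give a dosing instruction.

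Two general rules in Appendix 9 might seem to settle the matter. The rule to follow the most conservative recommendation is written for a participant with several different adverse events, not for conflicting rules on one event. The statement that Tables 26 and 27 are guidelines to be applied with clinical judgment does not extend to Section 8.3.6 or to note a. It could also be argued that the Hy's law text in Table 27 follows a Part-3 sentence and may be limited to Part-3; note a has no such limit, so the conflict remains in every Part.

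Four stronger readings are tempting and are not supported:

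- A reader might infer that a participant with only one raised transaminase falls into a gap and could be restarted. Case 2 above shows the opposite.
- Section 6.6.1.6 might be counted as a third vote for permanent discontinuation. It says "if there is evidence of severe injury, then discontinue treatment", without the word permanent, and the protocol recognises temporary discontinuation in Section 7.1.2.
- The Grade 3 stop sentence might be called a drafting error outright. Its condition is missing in the text available here, but tables were read by a program, and loss at that step cannot be excluded.
- A conflict with Table 26 might be claimed. Table 26 is general guidance, and hepatic events are referred to Table 27.

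**Conclusion.** The point holds in limited form. For possible Hy's law with both ALT and AST above 3 x ULN, Section 8.3.6 permits restart after recovery, while Appendix 2 note a (all Parts) and Table 27 require permanent discontinuation. The trigger difference is a consistency matter with little practical effect.

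The Table 27 Grade 3 AST/ALT paragraph gives incompatible actions. For Parts 1, 2 and 4, the clash between immediate and sequential holding of pembrolizumab is certain from the text. The clash created by the permanent-stop sentence depends on reading it literally, with no further condition, and is therefore less certain.

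This is an internal wording inconsistency that bears on participant safety. It should be corrected, but it does not touch the trial's design, sample size or analyses. How often it would matter cannot be estimated: the any-grade transaminase rates show that the laboratory signal is relevant to both small molecules, not how common severe events are.

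**What to change.** 1. In Section 8.3.6, replace the withhold sentence with permanent discontinuation of both study drugs. Change the trigger to AST or ALT above 3 x ULN and INR above 1.5, as in Section 4.1.1, Appendix 2 note a and Table 27.
2. In the Table 27 Grade 3 paragraph, have the sponsor confirm what condition the permanent-stop sentence was meant to carry. State the event or threshold and the Part it applies to, worded so that it does not contradict the Grade 4 text. Delete the sentence only if no such condition was intended: removing a stop rule of unclear intent should not be the default.
3. Leave one Grade 3 action per Part. For Part-3, keep what Table 27 already says: withhold both drugs, then reduce both SAR442720 and adagrasib by one level. Section 6.6.1.1 is not a substitute, because it refers back to Table 27 and, after recovery, mentions reduction of adagrasib only. For Parts 1, 2 and 4, keep the immediate hold of both drugs with pembrolizumab resumed at the same dose after recovery, and delete the sequential-hold sentence.

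The cost is wording in one bullet of Section 8.3.6 and one paragraph of one Table 27 row, plus one confirmation from the sponsor. Design, sample size and analysis are unchanged.
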